# 11.1.2 Visit 1 (Enrollment Procedures and IUD Insertion)

Potential participants will usually proceed to enrollment procedures immediately after successful screening (i.e., screening and enrollment visits can occur on the same day).

The protocol allows same-day enrollment and IUD insertion in these potential participants:

- Women not using hormonal contraception who are in the first 7 days of the menstrual cycle,
- Women who have been correctly and consistently using a reliable hormonal method of contraception before screening (OCs, patch, ring, implants) once these methods are stopped/removed,
- Women who have been using any type of IUD (same-day removal and study enrollment is acceptable),
- Women who are ≥ 30 days post uncomplicated medical abortion who have been consistently using a reliable hormonal method of contraception before screening (OCs, patch, ring) or have not had vaginal intercourse since pregnancy termination,
- Women who are ≥ 30 days post first, second or third trimester surgical abortion who have been consistently using a reliable hormonal method of contraception before screening (OCs, patch, ring) or have not had vaginal intercourse since pregnancy termination,
- Non-breastfeeding women who are ≥ 30 days post-delivery who have been consistently using a reliable hormonal method of contraception before screening (OCs, patch, ring) or have not had vaginal intercourse since pregnancy termination.

CCN016 Version #: 03.00 Version Date: 19Dec2018 Page 31 of 76

If enrollment cannot proceed for any reason, including a contraindicated infection or immediately post abortion/delivery, the potential participant should return no later than 60 days from the start of screening to be enrolled. If the potential participant was treated for a sexually transmitted infection, treatment should be complete and there should be no signs of active infection prior to enrollment. If the potential participant appears to have been re-infected, she would be considered a screen failure. If the potential participant was screened less than 30 days post-abortion or delivery, confirmation of eligibility should be completed prior to randomization including review for any new history, review of concomitant medications and urine pregnancy check. Review of cases that require a screening period longer than 60 days will occur on a case by case basis through a submitted waiver. If the enrollment visit occurs separately from screening, sites will reconfirm study eligibility prior to enrollment, including pregnancy testing. Study staff will collect adverse events (AEs) and any new or changed concomitant medications. Sites will randomize eligible women (at which point a woman will be considered enrolled) and women will receive one of the two study IUDs. Once enrolled, reimbursement for the women's time and scheduling of their 6-week contraceptive follow-up visit will occur.

**Table 03: Enrollment Visit Procedures** 

Component	Procedures
Administrative and Regulatory	
 
Randomize subject in EDC system and record required information on study product label
 

	
 
Provide reimbursement
 

	• Schedule next study visit (6 weeks out ± 5 days)
	
 
Review diary cards, including proper completion instructions. Distribute 2 daily diary forms; each form covers a 1-month period
 

CCN016 Version #: 03.00 Version Date: 19Dec2018 Page 32 of 76

Clinical	
 
If visit is separate from screening, reassess eligibility, including infection status, if treated, and risk of pregnancy
 
Assess for AEs and concomitant medication
 
Complete assessment of uterine cavity length by sound or pipelle. If cavity length measures less than 5.5 cm, subject must be discontinued and insertion should not be completed.
 
Collect information on subject's pain after speculum placement and prior to sounding of the uterus (baseline pain assessment)
 
Insert assigned IUD
 
Assess ease of insertion
 
Collect information on subject's pain after insertion (immediately and 10 minutes after insertion)
 

	
 
Insert assigned IUD
 
Assess ease of insertion
 
Collect information on subject's pain after insertion (immediately and 10 minutes after
 

	
 
Distribute Home Post Placement Pain Form for subjects to record their maximum daily pain for the 6 consecutive days following IUD placement, satisfaction with IUD and use of pain medications.
 

Laboratory Urin	e Test urine for pregnancy
5	• Retest for STIs if needed

**Note:** If enrollment does not immediately follow the screening procedure, confirmation of eligibility must be performed using clinical judgement to decide whether repeat pregnancy, STI testing, or other assessments are needed and if contact information should be reviewed. In addition, collection of information on AEs and concomitant medication changes will occur.

**Note**: At the discretion of the investigator, IUD insertion may be attempted a second time on the day of enrollment using the same device if no contamination issues occurred. If contamination occurred with the initial IUD on the day of enrollment, a second product may be obtained for insertion on same day of enrollment only. Procedures for obtaining second IUD will be outlined in the Health Decisions Study Manual. Reattempts using a different device or on a different date after enrollment are not allowed. Reinsertion post enrollment insertion is also not allowed.

Note: An Ultrasound does not need to be performed to confirm IUD placement.

Note: No anaesthesia may be used on first insertion attempt. Cervical anaesthesia only may be used if indicated per Investigator discretion for second insertion attempt on same day. Misoprostol is not allowed. Tenaculum site should not be anesthetized.

CCN016 Version #: 03.00 Version Date: 19Dec2018 Page 33 of 76

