#### 10.2.5.2 Urine pregnancy testing

Participants will undergo urine pregnancy testing at screening and enrollment (if enrollment occurs on a separate day from screening). A negative test is required to proceed with possible IUD placement. In addition, urine pregnancy tests will be administered during follow-up visits. Each facility will use the test kits and specific laboratories normally used for routine services at the facility's local laboratory.

Note: if urine pregnancy test is positive at screening, no further action is required and subject will become a screen failure. If positive urine pregnancy test report is based on home pregnancy test result post enrollment, subject should be scheduled to come in for an Unscheduled visit to have quantitative blood pregnancy test performed. If confirmatory quantitative blood pregnancy test comes back negative, then subject will be allowed to stay in the study.

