## Confidential

Study Procedures	Screening					Tr	eatment I	Period				Follow Up	Unscheduled
Visit Number	SCRN	V1	V2	V3	V4	C1	V5	C2	V6	С3	EXIT 	C4	UNS^
Treatment Period*	N/A	Day 1	6 Wks	3 Mos	6 Mos	9 Mos	12 Mos	18 Mos	24 Mos	30 Mos	37 Mos	17 Days	VAR
Unblind IUD to subject											X		
Continue/Remove IUD 											X		
Provide bridge contraception, as desired											X		
Complete final subject status form												X	
Diary cards dispensed (n) 		X	X	X	X								X
Diary cards reviewed/discussed			X	X	X		X						X
Diary cards collected (n) 			X	X	X		X						X
Other contraceptive use forms dispensed (n) 							X		X				X
Other contraceptive use forms reviewed								X	X	X	X		X
Other contraceptive use data captured (n) 								X	X	X	X		X
Prior & concomitant medications	X	X*	X	X	X		X		X		X		X
Adverse events		X	X	X	X	X	X	X	X	X	X	X	X
Home pregnancy test dispensed 		X	X	X	X		X		X		$X^6$		X
Blood Pregnancy Test 11													X

V = Visit; C = call; SCRN = Screening; UNS = Unscheduled; Wks = Weeks; Mos = Months; VAR = Varies;

CCN016 Version #: 03.00 Version Date: 19Dec2018 Page 62 of 76

\* If enrollment does not immediately follow the screening procedure, confirmation of eligibility must be performed and clinical judgment used to decide whether repeat pregnancy or other tests are needed and if contact information should be reviewed.

\* Visit Windows: If enrollment does not occur on same day as screening, subject should return no later than 60 days from start of screening to be enrolled. Post insertion: Visit 2= 6 wks  $\pm$  5 days, Visit 3= 3 mos  $\pm$  14 days, Visit 4= 6 mos  $\pm$  14 days, Call 1 = 9 mos  $\pm$  14 days, Visit 5 = 12 mos  $\pm$  14 days, Call 2 = 18 mos  $\pm$  14 days, Visit 6 = 24 mos  $\pm$  14 days, Call 3 = 30 mos  $\pm$  14 days, Exit = 37 mos  $\pm$  14 days). Call 4 = 17 days (+3) post removal.

^ During unscheduled visits, the Investigator will perform any study assessments as necessary to provide appropriate treatment.

<sup>1 Vital signs to include measurements of blood pressure, height, and weight.

<sup>2 Pelvic exam at screening will assess for the presence of any uterine or cervical anomalies that would preclude IUD use.

<sup>3 Next visit to be scheduled will be a phone call instead of an in-person office visit.

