## Confidential

-  Urine pregnancy test will be completed in clinic at Screening and during Enrollment prior to the subject being randomized to confirm subject is not pregnant prior to IUD placement if Enrollment occurs on a separate day from Screening.
-  During the Exit visit, the clinician will disclose which IUD the subject was using only after all IUD assessments are complete.
-  If the subject is using ParaGard, ask if she wishes to continue. If not, remove IUD. If the subject is using the test product, remove IUD.
-  Confirmatory quantitative blood pregnancy test should be done if initial urine pregnancy test comes back positive
-  A screening Pap test will be completed for subjects at screening if potential subject is not in compliance with normal standard of care guidelines regarding Pap testing. If additional testing or treatment is required based on Pap results, this should be completed prior to enrollment.
-  Visit 1 distribute 2 diary forms, Visit 2 distribute 2 diary forms, Visit 3 distribute 4 diary forms, and Visit 4 distribute 7 diary forms
-  Visit 2 collect 2 diary forms, Visit 3 collect 2 diary forms, Visit 4 collect 4 diary forms and Visit 5 collect 7 diary forms
-  Visit 5 and Visit 6 distribute 2 Other Contraceptive Use forms
-  Call 2, Visit 6, Call 3, and Exit collect data from Other Contraceptive Use forms
-  Includes subject's levels for pain and bleeding
-  Home pregnancy tests should be provided to subjects at Enrollment and then as needed at other visits with instructions for the subject to complete the test if there is any suspicion that they may be pregnant in between their study clinic visits.
-  Included as part of the Follow-Up Form assessments. At Call 1, Call 2 and Call 3, the follow up form is also referred to as the Telephone Follow Up Form since the Follow Up form information is collected by telephone.
-  Pain will be assessed immediately and 10 minutes after insertion

CCN016 Version #: 03.00 Version Date: 19Dec2018 Page 63 of 76

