7.3.1 Definition of variables

Pregnancy: The endpoint of the primary objective is incident pregnancy. The following data will be examined to determine whether a pregnancy has occurred:

- Positive pregnancy test result recorded on the Pregnancy Test, Pregnancy Notification, or Pregnancy Outcomes forms;
- Pregnancy otherwise reported on Adverse Event, IUD Removal or End of Trial forms.

Estimated Date of Conception (EDC): The Investigator will estimate the date of conception based upon results of transvaginal ultrasound examination, quantitative β -hCG determination, last menstrual period (per daily diary information), pelvic and/or abdominal examination, and pregnancy outcome.

Without looking at the treatment group assignment in the LiveTrial eCRF, the Medical Monitors will review the assigned date of conception and other relevant data to confirm the date of conception to be used for analysis. If the Medical Monitors assign a different date during this adjudication process, their reason for assigning a different date will be documented.

On-treatment Pregnancy: An on-treatment pregnancy is a pregnancy in which the EDC is 1) on or after the date of IUD insertion and 2) on or before 7 days of post IUD removal. In addition, a "worse case" scenario will be used that considers pregnancies as "on-treatment" if the EDC or date of expulsion is not known.

Study Cycle (28-day equivalent): Every 28 study days with information about whether the participant used other contraceptive methods within those 28 study days will be considered as a study cycle (e.g., study day 28 will be considered the end of cycle 1, and day 56 for the end of cycle 2, etc., so long as information on use of other methods is documented for those periods). Note: cycles where conception occurred or where a participant had the IUD removed will be considered 'study cycles' (even if the EDC or removal did not occur on the 28th day), so long as there is information on other contraceptive methods use up until the time of conception defined as an on-treatment pregnancy or IUD removal.

Study Cycles (described previously) with no diary data will be excluded from the pregnancy analysis. Two types of pregnancy analysis cycle will be used for the efficacy analysis:

Primary Pregnancy Analysis Cycle: A primary pregnancy analysis cycle is a study cycle that

- 1. contains an on-treatment pregnancy, or
- 2. has both these characteristics:
 - a. reported sexual intercourse in the cycle and

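### When enrolment falls on a later day than screening, the protocol both requires the repeat pregnancy test and leaves it to clinical judgement

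*Protocol*

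**What the plan says.** Two places in the protocol make the repeat test discretionary when enrolment does not immediately follow screening:

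- The note under Table 03 (section 11.1.2) calls for eligibility to be confirmed "using clinical judgement to decide whether repeat pregnancy, STI testing, or other assessments are needed".
- The asterisk footnote in Appendix 1 has "clinical judgment used to decide whether repeat pregnancy or other tests are needed". The Visit 1 cell of the urine pregnancy test row carries that asterisk.

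Three places require it:

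- Section 10.2.5.2: "Participants will undergo urine pregnancy testing at screening and enrollment (if enrollment occurs on a separate day from screening"). It adds that a negative result is needed before placement, without saying how recent the result must be.
- Section 11.1.2: "If the enrollment visit occurs separately from screening, sites will reconfirm study eligibility prior to enrollment, including pregnancy testing".
- Appendix 1 footnote 8, attached to the label of the same schedule row, places the test "during Enrollment prior to the subject being randomized to confirm subject is not pregnant prior to IUD placement" when the two visits fall on different days.

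The laboratory row of Table 03 also lists the urine test without condition, whereas the next line makes STI retesting conditional on need.

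The gap between visits may be up to 60 days, with longer gaps considered by waiver (section 11.1.2). Section 7.2 makes not being pregnant an inclusion criterion.

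**The concern.** Table 03 and the schedule of assessments are the parts of a protocol that site staff are likely to work from, and each holds both rules. A site that follows the discretionary text could randomise a woman and insert an IUD on a screening test some weeks old without seeing itself as deviating. A site that follows section 10.2.5.2 would not. The same inclusion criterion would then be applied differently across about 16 sites.

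Section 11.1 defers enrolment for women at risk of pregnancy in the current cycle, so the women affected include some deferred for exactly this reason. The next scheduled clinic test is at six weeks.

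The stakes are first eligibility and safety. They touch the primary analysis because its endpoint is pregnancy, the number of events is expected to be small, and a Visit 1 result is one piece of evidence on whether a conception preceded insertion.

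**Working it through.** **The text.** For a woman enrolled on a later day:

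| Place in protocol | Repeat urine test |
|---|---|
| Table 03, note | Clinical judgement |
| Appendix 1, asterisk footnote (on the Visit 1 cell) | Clinical judgement |
| Section 10.2.5.2 | Required |
| Section 11.1.2 | Required |
| Appendix 1, footnote 8 (on the row label) | Required |
| Table 03, laboratory row | Listed, no condition |

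The asterisk also marks a visit-window footnote in Appendix 1, but that one belongs to the treatment-period header row. On the Visit 1 cells the natural reading is the footnote about delayed enrolment. The schedule row therefore carries both rules at once. Nothing in the protocol says which passage prevails.

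**The route to the endpoint.** SAP 7.3.1 counts a pregnancy as on-treatment if the estimated conception date is on or after insertion and no later than 7 days after removal. The Medical Monitors confirm the date without looking at the assignment. Protocol 6.1 has pregnancies diagnosed soon after insertion reviewed before they are called method failures. A pregnancy that began before insertion is thus counted only in two cases:

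1. Its date is unknown. The SAP's worst-case provision treats a pregnancy as on-treatment "if the EDC or date of expulsion is not known".
2. Its date is wrongly placed on or after insertion.

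Either error would raise the Pearl Index, against the test product.

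**Size of one event.** Inputs: about 17,700 cycles for 800 women (protocol 19.1) and the SAP 7.3.2 formulas, with x pregnancies in C cycles:

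- Pearl Index = 1300 × x / C
- Upper limit = 1300 × χ²(0.975; 2(x+1)) / (2C)
- Lower limit = 1300 × χ²(0.025; 2x) / (2C)

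The cycle count reproduces. It is 800 × 0.90 (women under 36) × 13 × 0.843 × (1 − e^(−rT))/r, with r = 0.2 or −ln 0.8 and T = 3 or 37/12 years. The four combinations give 17,256 to 18,158. The synopsis footnote also adds up: 7,100 + 5,700 + 4,900 = 17,700.

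Table 09 at x = 6 reproduces: index 1300 × 6/17,700 = 0.441, interval 0.162 to 0.959, against the stated 0.4 (0.2 to 1.0).

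One added event gives the following. The 880-woman cycle count is an assumption, scaled pro rata: 17,700 × 880/800 = 19,470.

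| Cycles | Events | Pearl Index | Upper limit |
|---|---|---|---|
| 17,700 | 6 → 7 | 0.441 → 0.514 | 0.959 → 1.059 |
| 19,470 (assumed) | 6 → 7 | 0.401 → 0.467 | 0.872 → 0.963 |

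Six is only the last row of Table 09, not a forecast. At 17,700 cycles the upper limit rises by 0.14 for a first event (0.271 to 0.409) and by 0.10 for an eighth (1.059 to 1.158).

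**The case against.** The best reply is that this is a wording slip with several safeguards behind it. Table 03's own laboratory row lists the test, and its clinical row requires pregnancy risk to be reassessed when the visit is separate. Footnote 8 is already on the schedule row. For women screened less than 30 days after abortion or delivery, section 11.1.2 separately names a urine pregnancy check. Pregnancy risk is only one reason for deferral; infection and awaited Pap results are others. Home tests are handed out at enrolment, and a clinic test follows at six weeks. Protocol section 13 lists ultrasound, quantitative hCG, last menstrual period, examination and outcome for dating, with the investigator's estimate as a last resort, so an unknown date should be uncommon. It is also unclear whether the SAP's provision for unknown dates belongs to the primary count at all.

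Most of this stands, and it limits the effect on the endpoint. It does not remove the contradiction: the two discretionary texts name the pregnancy test explicitly. Nor does it make the dating evidence complete. The diary that supplies the last menstrual period is first handed out at Visit 1 and so holds no record from before insertion.

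A reader might infer that pre-existing pregnancies will flow into the primary endpoint, or that one such case would push the result past a limit of 1.0. The documents support neither. The on-treatment definition and the adjudication stand in the way. The figure of about 1.0 in section 19.1 describes precision at six events, not a success criterion. With the assumed 880-woman cycle count, going from six to seven events stays below 1.0.

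**Conclusion.** The contradiction is real, sits in the current protocol text, and needs no calculation to establish. It is chiefly an inconsistency in eligibility and safety procedure, with a narrow path to the primary endpoint through an unknown or mistaken conception date.

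The Pearl Index figures show only how sensitive the estimate is to a single event; they are not an expected bias. They rest on the protocol's planned cycles and on one pregnancy being wrongly counted. The documents give neither the number of later-day enrolments nor any rate of misdating, so no expected effect can be calculated. The point is worth correcting because it bears on an inclusion criterion and the correction is small.

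**What to change.** Reconcile the Table 03 note, the Appendix 1 asterisk footnote and the asterisk on the Visit 1 pregnancy-test cell with section 10.2.5.2, section 11.1.2 and footnote 8, so that one rule applies at every site. Which rule that should be is a clinical decision for the sponsor and is not judged here.

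For women already enrolled on a later day than screening, check whether a Visit 1 pregnancy test result is recorded. Do this before conception dates are adjudicated, and tell the Medical Monitors where no result exists.

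The cost is a few words in a table note, a footnote and a schedule cell, plus one data listing that compares screening and enrolment dates with recorded test results. No analysis method changes.

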# 11.2 Clinic-Based Follow-up Visits

At 6-weeks, 3-months, 6-months, 12-months, 24-months, and 37-months post-insertion, all participants will return for follow-up visits (Table 04). During these visits, collection of information on AEs, concomitant medications, IUD acceptability, and potential concerns or side effects related to the study product will occur. To verify the presence of the IUD, the clinician will check for the IUD strings using a visual inspection, digital palpation and/or sweep for strings using a cytobrush. If the IUD strings are not visible or palpable, or if there is clinical suspicion of expulsion, clinicians will proceed with an ultrasound examination to verify that the IUD is in position (Section 9.7, Appendix 2). Participants will be scheduled for their next follow-up visit or call. Staff will also encourage participants to return to the clinic for adverse events or any other concerns at any time. If at any visit the Investigator determines that a participant should be discontinued, follow Early Discontinuation Visit procedures (Section 11.5).

#### 11.2.1 Visit 2 (6-weeks post-insertion $\pm$ 5 days)

Study staff will collect AEs and new or changed concomitant medications, collect and review diaries with the participants, ask IUD acceptability questions, and complete the follow-up assessment forms. Clinicians will check for IUD strings as above. Assess (and treat as applicable) for STIs/RTIs, as well as check for pregnancy. Participants will be reimbursed and be scheduled for their 3-month follow-up visit. Reconfirm participant's contact information.

# 11.2.2 Visit 3 (3 months post-insertion $\pm$ 14 days)

Study staff will collect AEs and new or changed concomitant medications, collect and review diaries with the subjects, ask IUD acceptability questions, and complete the follow-up assessment forms. Clinicians will check for IUD strings as above. Assess (and treat as applicable) for STIs/RTIs, as well as check for pregnancy. Participants will be reimbursed and be scheduled for their 6-month follow-up visit. Reconfirm participant's contact information.

